#### 4. CHANGES IN THE PLANNED ANALYSIS OF THE STUDY

The trial part 1 was performed according to the CTP and the trial was terminated before any subject in trial part 2 was treated. Therefore, the analysis described in this TSAP refers to trial part 1 only.

All analyses described in this TSAP are in accordance with the statistical methods described in the revised CTP.

#### 5. ENDPOINTS

#### 5.1 PRIMARY ENDPOINT

The primary endpoint is a PK endpoint of BI 894416, as defined in Section 2.1.2 of the CTP:

•  $AUC_{0-\infty}$  (area under the concentration-time curve of the analyte in plasma over the time interval from 0 extrapolated to infinity)

#### 5.2 SECONDARY ENDPOINT

#### 5.2.1 Key secondary endpoint

Not applicable

#### 5.2.2 Secondary endpoint

The secondary endpoint is a PK endpoint of BI 894416, as defined in **Section 2.1.2 of the CTP**:

•  $AUC_{0-tz}$  (area under the concentration-time curve of the analyte in plasma over the time interval from 0 the last quantifiable time point)

#### 5.3 FURTHER ENDPOINTS

#### 5.3.2 Safety parameters

Safety and tolerability of BI 894416 will be assessed based on further safety endpoint defined in **Section 2.2.2.2 of the CTP**:

- Adverse events (including clinically relevant findings from the physical examination)
- Safety laboratory tests
- 12-lead ECG
- Vital signs (blood pressure, pulse rate)

#### 5.4 OTHER VARIABLES

### 5.4.1 Demographic and other baseline characteristics

CTP Section 5.2.1: At screening, the medical examination will include demographics, height and body weight, smoking and alcohol history (alcohol history results are not mandatory to be entered into CRF or to be reported), relevant medical history and concomitant therapy, review of inclusion and exclusion criteria, review of vital signs (BP, PR), 12-lead ECG, laboratory tests, and a physical examination.

TSAP for BI Trial No: 1371-0022

Proprietary confidential information © 2021 Boehringer Ingelheim International GmbH or one or more of its affiliated companies

Age (years) will be determined as the difference between year of birth and year of informed consent.

Body mass index will be calculated as weight (kg) / (height (m)).

#### 5.4.2 Treatment compliance and treatment exposure

Treatment compliance will not be analysed as a specific endpoint, cf. Section 4.3 of the CTP.

Since only single doses will be applied per treatment period, the date and time of drug administration along with measured drug plasma concentrations will ensure treatment exposure.

#### 6. GENERAL ANALYSIS DEFINITIONS

#### 6.1 TREATMENTS

For basic study information on treatments to be administered, assignment of treatment groups, and selection of doses, cf. Section 4 of the CTP.

The trial is divided into two parts but only trial part 1 was performed.

In **trial part 1**, each subject is planned to be treated in five subsequent treatment periods (five-period cross-over) with one single dose in each treatment period followed by one single dose in a sixth treatment period in a fixed sequence.

Treatments in the five-period cross-over:

- Reference treatment 1 (R1) 60mg tab IR fasted: 60 mg of BI 894416, IR tablets under fasted conditions
- Test treatment 1 (T1) 62.5mg tab FRR fasted:
   62.5 mg of BI 894416, ER tablet (fast release rate) under fasted conditions
- Test treatment 2 (T2) 62.5mg tab SRR fasted:
   62.5 mg of BI 894416, ER tablet (slow release rate) under fasted conditions
- Test treatment 3 (T3) 62.5mg cap FRR fasted:
   62.5 mg of BI 894416, ER capsule (fast release rate) under fasted conditions
- Test treatment 4 (T4) 62.5mg cap SRR fasted:
   62.5 mg of BI 894416, ER capsule (slow release rate) under fasted conditions

Each subject is planned to be randomly allocated to one of five treatment sequences (T3-R1-T1-T4-T2, T2-T1-T3-R1-T4, T4-T3-R1-T2-T1, T1-T4-T2-T3-R1 and R1-T2-T4-T1-T3, cf. Table 6.1: 2).

Treatments in the fixed sequence:

- Test treatment 5 (T5) 62.5mg tab SRR fed:
   62.5 mg of BI 894416 ER, tablet (slow release rate) after a high fat breakfast
- Test treatment 6 (T6) 62.5mg cap SRR fed:
   62.5 mg BI 894416, capsule (slow release rate) after a high fat breakfast

Subject will be randomly allocated to either T5 or T6, stratified by sequence (cf. Table 6.1: 2 for an overview of the treatment sequences).

For statistical analysis of AEs, safety laboratory data and vital signs, the following analysis phases are defined for each subject:

Table 6.1: 1 Flow chart of analysis phases for statistical analyses of AEs

Study analysis phase	Label	Start (inclusive)	End (exclusive)
Screening	Screening	Date of informed consent	Date/time of administration of BI 894416 in any formulation
On-treatment	BI 894416 respectively	Date/time of administration of BI 894416 in any formulation	Date/time of administration of BI 894416 in another formulation or 12:00 a.m. on day after subject's trial termination date, whichever occurs earlier

Analysis phases for statistical analysis of AEs are defined for each subject as described in the table above.

CTR Section 15, Appendix 16.1.13.1.8.2 and Appendix 16.1.13.1.8.3 AE displays will present results for the on-treatment phase only.

In disposition, demographics and baseline characteristics, all subjects will be analysed together (i.e., one "BI 894416" column). Exposure will be summarised by period and treatment formulation.

The statistical analyses of safety laboratory tests and vital signs will be performed including all subject together (i.e., one "BI 894416" column), with clear differentiation between baseline (cf. Section 6.7) and on-treatment measurements.

Table 6.1: 2 Overview of treatment sequences

Trial part 1
T3-R1-T1-T4-T2-T5
T3-R1-T1-T4-T2-T6
T2-T1-T3-R1-T4-T5
T2-T1-T3-R1-T4-T6
T4-T3-R1-T2-T1-T5
T4-T3-R1-T2-T1-T6
T1-T4-T2-T3-R1-T5
T1-T4-T2-T3-R1-T6
R1-T2-T4-T1-T3-T5
R1-T2-T4-T1-T3-T6

More details on the technical implementation of these analyses are provided in the ADS Plan of this TSAP.

TSAP for BI Trial No: 1371-0022

Proprietary confidential information © 2021 Boehringer Ingelheim International GmbH or one or more of its affiliated companies

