7.3.4 Safety analyses

Safety will be analysed based on the assessments described in Section [2.2.2.2](#). All treated subjects (TS, refer to Section [7.2](#)) will be included in the safety analysis. Safety analyses will be descriptive in nature and based on BI standards. No statistical comparison between treatment groups for safety data is planned, unless otherwise specified within the relevant section.

For all analyses, the treatment actually administered (= treatment at onset) to the subject will be used (any deviations from the randomised treatment will be discussed in the minutes of the Report Planning Meeting).

Treatments will be compared in a descriptive way. Tabulations of frequencies/ proportions will be used to evaluate categorical (qualitative) data, and tabulations of descriptive statistics will be used to analyse continuous (quantitative) data.

Measurements (such as ECG, vital signs, or laboratory parameters) or AEs will be assigned to treatments (refer to Section [4.1](#)) based on the actual treatment at the planned time of the measurement or on the recorded time of AE onset (concept of treatment emergent AEs). Therefore, measurements planned or AEs recorded prior to first intake of trial medication will be assigned to the screening period, those between first trial medication intake and end of REP (refer to Section [1.2.3](#)) will be assigned to the treatment period. Events occurring after the REP but prior to next intake or end of trial termination date will be assigned to 'follow-up'. In case of two or more treatments, the follow-up will be summarized according to the previous treatment. These assignments including the corresponding time intervals will be defined in detail in the TSAP. Note that AEs occurring after the last per protocol contact but entered before final database lock will be reported to Pharmacovigilance only and will not be captured in the trial database.

Additionally, further treatment intervals (analysing treatments) may be defined in the TSAP in order to provide summary statistics for time intervals, such as combined treatments, on-treatment totals, or periods without treatment effects (such as screening and follow-up intervals).

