Adverse events will be coded using the Medical Dictionary for Regulatory Activities (MedDRA). Frequency, severity, and causal relationship of AEs will be tabulated by treatment, system organ class, and preferred term. SAEs, AESIs (refer to Section [5.2.6.1](#)), and other significant AEs (according to ICH E3) will be listed separately.

Previous and concomitant therapies will be presented per treatment group without consideration of time intervals and treatment periods.

Laboratory data will be compared to their reference ranges. Values outside the reference range as well as values defined as possibly clinically significant will be highlighted in the listings. Additionally, differences from baseline will be evaluated.

Vital signs or other safety-relevant data will be assessed with regard to possible on-treatment changes from baseline.

Relevant ECG findings will be reported as AEs.

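### The SAP drops the protocol's REP and follow-up phases and pools laboratory and vital-sign summaries, yet declares full accordance with the protocol

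*SAP*

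**What the plan says.** **Protocol 7.3.4** sets three phases. Screening runs to first intake and the treatment period runs to the end of the REP. After that, "Events occurring after the REP but prior to next intake or end of trial termination date will be assigned to" follow-up. It adds: "In case of two or more treatments, the follow-up will be summarized according to the previous treatment". Safety data are handled by treatment: "Measurements (such as ECG, vital signs, or laboratory parameters) or AEs will be assigned to treatments", using the actual treatment at the planned measurement time or at AE onset, and "Treatments will be compared in a descriptive way". Tabulation by treatment is prescribed in so many words only for AEs: "Frequency, severity, and causal relationship of AEs will be tabulated by treatment, system organ class, and preferred term". Two sentences refer to the SAP: "These assignments including the corresponding time intervals will be defined in detail in the TSAP", and "Additionally, further treatment intervals (analysing treatments) may be defined in the TSAP in order to provide summary statistics", with combined treatments and on-treatment totals as examples.

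**SAP 6.1, Table 6.1: 1** defines two phases, screening and on-treatment, for AEs, laboratory data and vital signs. On-treatment starts at an administration and ends at "Date/time of administration of BI 894416 in another formulation or 12:00 a.m. on day after subject's trial termination date, whichever occurs earlier". SAP 7.8.1 places every AE in one of these two phases. SAP 6.1 then summarises laboratory tests and vital signs for all subjects together in a single BI 894416 column. The public SAP text mentions neither the REP nor a follow-up phase.

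**SAP section 4** reports that part 2 was not run and states that all analyses accord with the statistical methods of the revised protocol.

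**The concern.** Two features of the protocol's safety analysis disappear without being declared: the split between time within and after the REP, and the by-treatment view of laboratory values and vital signs.

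The second has the more concrete consequence. Part 1 compares one immediate-release (IR) reference with four extended-release (ER) treatments, and a descriptive safety comparison should let a reader see whether values move differently under IR and ER. One pooled column cannot show that.

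The first affects how on-treatment AE counts are read, because events after the REP would be counted together with events within it. Someone relying on SAP section 4 would not know that either change had been made.

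**Working it through.** The documents give no figure to reproduce. The check is a comparison of text, then arithmetic on windows and on the mix of treatments per period.

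**1. Phases side by side**

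| | Protocol 7.3.4 | SAP 6.1 and 7.8.1 |
|---|---|---|
| Before first dose | Screening | Screening |
| Dose to end of REP | Treatment | On-treatment |
| End of REP to next dose or trial end | Follow-up, under previous treatment | On-treatment, same treatment |
| Laboratory values, vital signs | Assigned to treatment, compared descriptively | Phases defined by treatment, summary pooled |

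I read the protocol's treatment period dose by dose, because its follow-up sentence refers to the next intake. Each AE then stays under the same treatment in both documents; only the phase label can differ.

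**2. How much time changes label**

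Inputs: doses at least 4 days apart, dosing at 08:00, and end-of-trial (EoT) visit on Day 8 to 15 (protocol Flow Chart, part 1). Assumptions: the EoT day is counted from the period 6 dose, the EoT date is the termination date, and spacing is exactly 4 days. The protocol refers to Section 1.2.3 for the REP. That section is not in the public text, so the REP length r is varied from 1 to 15 days.

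- SAP window, periods 1–5: 4 days each.
- SAP window, period 6: (EoT day − 1) + 16/24 = 7.67 days (Day 8) or 14.67 days (Day 15).
- SAP on-treatment total: 5 × 4 + 7.67 = 27.67 days, or 5 × 4 + 14.67 = 34.67 days.
- Days the protocol would call follow-up: max(0, 4 − r) in each of periods 1–5, and max(0, 7.67 − r) to max(0, 14.67 − r) in period 6.

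| r (days) | Each of periods 1–5 | Period 6 | Total per subject |
|---|---|---|---|
| 1 | 3 | 6.67–13.67 | 21.67–28.67 (78–83%) |
| 3 | 1 | 4.67–11.67 | 9.67–16.67 (35–48%) |
| 4 | 0 | 3.67–10.67 | 3.67–10.67 (13–31%) |
| 7 | 0 | 0.67–7.67 | 0.67–7.67 (2–22%) |
| 15 | 0 | 0 | 0 |

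The effect therefore runs from large to none, depending on a length that cannot be read here.

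**3. What a pooled table by period can show**

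The treatments of the five sequences (protocol 3.1 and 7.6), read down each period:

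- Period 1: T3, T2, T4, T1, R1
- Period 2: R1, T1, T3, T4, T2
- Period 3: T1, T3, R1, T2, T4
- Period 4: T4, R1, T2, T3, T1
- Period 5: T2, T4, T1, R1, T3

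Each period holds every fasted treatment once. With equal allocation, a mean change d that occurs only under R1 contributes d/5 to each of the five period means, so no contrast among periods 1–5 reveals it. Allocation cannot be exactly equal, since 24 is not a multiple of 5. If the blocks are of 10 (assumed), two full blocks plus any 4 of a third give 4 to 6 subjects per five-period sequence. R1 is then 4/24 to 6/24 (17–25%) of each period, and two periods differ by at most (6 − 4)/24 × d = 0.08d. Fed treatments occur only in period 6, so fed against fasted is visible only as period 6 against earlier periods, confounded with time.

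**The case against.** **Delegation.** The protocol leaves the intervals to the SAP and foresees combined treatments. That much is true. But the SAP is asked to detail the stated assignments, and the combined intervals are introduced as additions. Neither sentence covers removing a phase or showing only the pooled summary.

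**By-treatment laboratory tables are not prescribed.** This carries weight. The protocol's explicit by-treatment tabulation is for AEs; for laboratory values and vital signs the expectation rests on the assignment sentence together with the sentence on descriptive comparison. This is the weaker limb.

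Stronger readings that a reader might infer, and why they fail:

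- *The SAP abandons treatment assignment for laboratory values and vital signs.* Table 6.1: 1 defines treatment phases for them; only the summary display is pooled.
- *AEs are lost, misattributed or impossible to separate by timing.* The protocol credits follow-up to the previous treatment, so attribution is unchanged. AE onset times are recorded, individual values are listed, and clinically relevant findings still become AEs.
- *The SAP creates the longer T5/T6 window (7.67–14.67 days against a 4-day minimum).* The protocol gives the last treatment the same total span once follow-up is included. Restoring the REP equalises on-treatment windows only if the REP is no longer than the interval between doses; at 7 days it would still be 7 against 4.
- *The laboratory shift table uses only the EoT sample.* SAP 7.8.2 refers to the last value on treatment, which may mean one value per subject or one per phase. The text does not settle it.
- *A fasted phase would not end at the fed dose of the same formulation.* In two of the ten sequences T5 directly follows T2, or T6 follows T4. SAP 7.4.1 uses the word formulations for these treatments, so another treatment is probably meant. This is a wording ambiguity only.

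**Conclusion.** The conflict stands on the text. The SAP omits the REP limit and the follow-up phase, summarises laboratory values and vital signs in one column, and is wrong to declare full accordance on these points.

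The firm consequence is that the laboratory and vital-sign summary tables cannot compare IR with ER, and show fed against fasted only through period. The consequence for AE tables is undetermined: at 4-day spacing, between 0 and 28.67 days per subject change label for an assumed REP of 1 to 15 days. The absence of the REP length from the public text is not itself a fault of the plan.

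Severity is minor. Only descriptive safety tables are affected, and the protocol plans no statistical comparison of safety between treatments. The pharmacokinetic analyses are untouched.

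**What to change.** 1. Show descriptive statistics for laboratory values and vital signs by treatment (R1, T1 to T6) at the scheduled time points common to all treatments, keeping the pooled column as a total. If the laboratory shift table is also given by treatment, base it on the 24 h sample, which is scheduled after every dose. The last value in each phase would not be like for like, because the 72 h laboratory sample is taken only before discharge at visit 7 (Flow Chart, part 1, footnote 10).
2. In Table 6.1: 1, end each on-treatment phase at the earliest of end of REP, next administration of BI 894416 (any treatment) or trial end, and summarise follow-up under the previous treatment. This also removes the formulation ambiguity.
3. If either departure is kept, declare it with reasons in SAP section 4 and correct the accordance statement.

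Cost: SAP wording and some re-programming of standard tables, with no new data. The tables widen from 1 to 8 columns (seven treatments plus total). T5 and T6 would have about 12 subjects each (10 to 14 if blocks of 10), so those columns will be sparse. Declaring the departures instead takes a few sentences.

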4.1.1 Identity of the Investigational Medicinal Products

Trial part 1

The characteristics of the test product are given below:

Name: ***T1- Prototype Formulation A2 (ER tablet - fast release rate)***

Substance: BI 894416

Pharmaceutical formulation: Tablet

Source: [REDACTED]

Unit strength: 62.5 mg

Posology: 1-0-0

Route of administration: Oral with 240 mL of water after an overnight fast of at least 10 h

Duration of use: One day (single dose) for each treatment

Name: ***T2 & T5/ Prototype Formulation C2(ER tablet – slow release rate)***

Substance: BI 894416

Pharmaceutical formulation: Tablet

Source: [REDACTED]

Unit strength: 62.5 mg

Posology: 1-0-0

Route of administration: Oral with 240 mL of water after an overnight fast of at least 10 h or (T2)

Oral with 240 mL of water following a high-fat high-calorie breakfast (T5)

Duration of use: One day (single dose) for each treatment

Proprietary confidential information © 2020 Boehringer Ingelheim International GmbH or one or more of its affiliated companies

Name: ***T3- Prototype Formulation D2(ER capsule – fast release rate)***

Substance: BI 894416

Pharmaceutical formulation: Capsule

Source: [REDACTED]

Unit strength: 62.5 mg

Posology: 1-0-0

Route of administration: Oral with 240 mL of water after an overnight fast of at least 10 h

Duration of use: One day (single dose) for each treatment

Name: ***T4 & T6- Prototype Formulation F2 (ER capsule – slow release rate)***

Substance: BI 894416

Pharmaceutical formulation: Capsule

Source: [REDACTED]

Unit strength: 62.5 mg

Posology: 1-0-0

Route of administration: Oral with 240 mL of water after an overnight fast of at least 10 h or
Oral with 240 mL of water following a high-fat high-calorie breakfast

Duration of use: One day (single dose) for each treatment

The characteristics of the reference product are given below:

Name: ***R1-Reference Formulation 1 (IR tablet)***

Substance: BI 894416

Pharmaceutical formulation: Tablet

Source: [REDACTED]

Unit strength: 10 mg

Posology: 6-0-0

Route of administration: Oral with 240 mL of water after an overnight fast of at least 10 h

Duration of use: One day (single dose) for each treatment

Proprietary confidential information © 2020 Boehringer Ingelheim International GmbH or one or more of its affiliated companies

Trial part 2 (optional)

Name: ***T7 & T8/ Prototype Formulation G or I(optimized ER tablet or ER capsule formulation)***

Substance: BI 894416

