#### 7.2 CONCOMITANT DISEASES AND MEDICATION

Concomitant diseases will be coded according to the most recent version of MedDRA. Concomitant medication will be coded according to the most recent version of the World Health Organisation – Drug Dictionary. Concomitant non-drug therapies will be coded according to the most recent version of MedDRA.

A medication will be considered concomitant, if it

- is ongoing at the time of first study drug administration, or
- starts within the analysis phase of the respective treatment (see Section 6.1 for a definition of treatments and analysis phases).

The relevance of the concomitant therapies to the evaluation of PK will be decided no later than at the RPM.

Only descriptive statistics are planned for this section of the CTR.

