#### 7.8.1 Adverse Events

AEs will be coded with the most recent version of MedDRA.

The analyses of AEs will be descriptive in nature. All analyses of AEs will be based on the number of subjects with AEs and not on the number of AEs.

For further details on summarization of AE data, please refer to "Analysis and Presentation of Adverse Event Data from Clinical Trials" (7) and "Handling of missing and incomplete AE dates" (3).

The analysis of AEs will be based on the concept of treatment emergent AEs. That means that all AEs will be assigned to screening or on-treatment phase as defined in Section 6.1. AEs will be analysed based on actual treatments, as defined in Table 6.1: 1.

An overall summary of AEs will be presented. This overall summary will comprise summary statistics for the class of AESIs.

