#### **CTP Section 5.2.6.1.4:** *The following are considered as AESIs:*

#### • *Hepatic injury*

A hepatic injury is defined by the following alterations of hepatic laboratory parameters:

- An elevation of AST (aspartate transaminase) and/ or ALT (alanine transaminase) ≥3-fold ULN combined with an elevation of total bilirubin ≥2fold ULN measured in the same blood sample, or
- $\circ$  Aminotransferase (ALT, and/ or AST) elevations  $\geq 10$  fold ULN

The investigator had to classify on the eCRF whether an observed AE was an AESI or not.

According to ICH E3 (8), in addition to deaths and SAEs, "other significant" AEs need to be listed in the clinical trial report. These will be any non-serious adverse event that led to an action taken with study drug (e.g. discontinuation or dose reduced or interrupted).

The frequency of subjects with AEs will be summarised by treatment, primary SOC and preferred term. AEs which were considered by the investigator to be drug related will be summarised separately. Separate tables will also be provided for subjects with SAEs and subjects with AESIs. AEs will also be summarized by maximum intensity.

The SOCs and preferred terms within SOCs will be sorted by descending frequency over all treatment groups.

For disclosure of AE data on ClinicalTrials.gov, the frequency of subjects with non-serious AEs occurring with an incidence of greater than 5 % (in preferred terms) will be summarised by treatment, primary SOC and preferred term. The frequency of subjects with SAEs will also be summarised.

For disclosure of AE data in the EudraCT register, the frequency of AEs, the frequency of non-serious AEs with an incidence of greater than 5 % (in preferred terms) and the frequency of SAEs will be summarized.

For support of lay summaries, the frequency of subjects with drug-related SAEs will be summarized by treatment, primary SOC and preferred term.

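### Read literally, SAP Table 6.1: 1 leaves the fasted AE phase open through the fed period in two of the ten sequences, because the fed dose is the same formulation

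*SAP*

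**What the plan says.** SAP 6.1, Table 6.1: 1, starts an on-treatment phase at a dose of BI 894416 in any formulation. The phase ends at "Date/time of administration of BI 894416 in another formulation" or, if earlier, at midnight after the subject's trial termination date.

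The phases feed the adverse-event tables. SAP 7.8.1 states that "AEs will be analysed based on actual treatments, as defined in" that table, and that "The frequency of subjects with AEs will be summarised by treatment, primary SOC and preferred term". T2 and T5, and T4 and T6, are separate treatments in those tables.

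Protocol 4.1.1 gives one product entry to each pair. The tablet entry is headed "T2 & T5/ Prototype Formulation C2(ER tablet – slow release rate"), and the slow-release capsule, F2, is shared in the same way by T4 and T6. The only difference within a pair is fasting versus the high-fat breakfast.

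SAP Table 6.1: 2 lists ten sequences, including "T3-R1-T1-T4-T2-T5" and "T2-T1-T3-R1-T4-T6".

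Protocol 7.3.4 assigns events to the treatment actually given at onset, bounds the interval after the residual effect period by the next intake, and leaves the exact intervals to the SAP.

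**The concern.** The SAP is where the protocol expects the intervals to be exact. The end rule is keyed to a change of formulation, whereas the tables are keyed to treatment, and the two differ when the same product is given first fasted and then fed in consecutive periods. The fed dose opens its own phase but, read literally, does not close the fasted one.

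Any event with onset after that fed dose would then count under both treatments. The treatments that gain events are T2 and T4, the fasted counterparts of the fed arms, so the descriptive fasted-versus-fed AE picture would be blurred. T2 and T4 would also carry a longer observation time in these subjects than in the others. Two programmers who both follow the text could produce different T2 and T4 columns.

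**Working it through.** The plan gives no figure on this point, so the check is to apply the end rule to each sequence and count.

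**Inputs.** Formulations (Protocol 4.1.1): R1 = IR tablet, T1 = A2, T2 = T5 = C2, T3 = D2, T4 = T6 = F2. Sequences: SAP Table 6.1: 2, allocated equally (Protocol 7.6). Subjects in part 1: 24 (Protocol 7.7).

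**Step 1: does the period 5 phase close at the period 6 dose?** Within periods 1 to 5 every treatment is a different formulation, so all earlier phases close at the next dose. Only the step from period 5 to period 6 can fail.

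| First five periods | Period 5 | Then T5 (C2) | Then T6 (F2) |
|---|---|---|---|
| T3-R1-T1-T4-T2 | C2 | **stays open** | closes |
| T2-T1-T3-R1-T4 | F2 | closes | **stays open** |
| T4-T3-R1-T2-T1 | A2 | closes | closes |
| T1-T4-T2-T3-R1 | IR | closes | closes |
| R1-T2-T4-T1-T3 | D2 | closes | closes |

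The result is 2 of 10 sequences, one affecting T2 and one affecting T4.

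**Step 2: subjects.** Under equal allocation the expected number is 24 x 2/10 = 4.8, or 2.4 for each of T2 and T4.

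The block size is not stated. If it is 10, then 24 = 2 x 10 + 4. Two full blocks put 2 x 2 = 4 subjects in the affected sequences, and the first four places of a third block add k more with probability C(2,k) x C(8,4-k) / C(10,4):

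- k = 0: 70/210 = 0.33
- k = 1: 112/210 = 0.53
- k = 2: 28/210 = 0.13

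That is 4 to 6 of 24 subjects (17% to 25%), or 2 or 3 of 24 for each of T2 and T4. Two full blocks of 10 also give exactly 10 subjects on each of T5 and T6, which fits the protocol's minimum of 10 per fed arm but does not prove the block size.

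**Step 3: length of the open phase.** Assume the minimum 4 days between doses, dosing at about 08:00, and termination at the end-of-trial visit on Day 8 to 15 of period 6. The period 5 phase should last 4 days. Read literally, it lasts from 4 + 7 + 16/24 = 11.7 days to 4 + 14 + 16/24 = 18.7 days.

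**Step 4: what one event can do to a table.** With 24 subjects on T2 or T4, one subject is 1/24 = 4.2% and two are 2/24 = 8.3%. If the 5% disclosure cut-off in SAP 7.8.1 is applied within a treatment, one carried-over event could lift a preferred term that one other subject already has above it.

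**Step 5: after the change.** If each phase ends at the next administration, 0 of 10 sequences overlap.

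**The case against.** The strongest reply is that the SAP does not use *formulation* strictly. SAP 7.4.1 glosses treatment as formulation and then calls T5 a formulation to be compared with T2; SAP 7.4.2 repeats the gloss. In that vocabulary the fed dose is another formulation, every phase closes at the next dose, and nothing is wrong. The protocol's treatment-at-onset rule, the reference in SAP 7.8.1 to actual treatments, and the SAP's statement that it accords with the protocol all point the same way. The dataset specification to which SAP 6.1 refers for technical detail is not available and may settle the matter.

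This stands as evidence of intent, but it does not make the wording clear. The synopsis lists C2 and F2 each as one test product with two modes of administration, Protocol 7.4 distinguishes formulations from fasted or fed administration, and SAP 7.4.2 treats the comparison of formulations and the comparison of fed with fasted as separate analyses. The narrow reading is at least as natural. The trial-termination limit does not help, because it falls after the fed dose.

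It is also fair to say that the safety analysis is descriptive, that no statistical comparison between treatments is planned for it, and that individual events remain visible in the listings. The subject count is the number whose phase boundary could be wrong; the number of misassigned events may be smaller or zero.

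A reader might infer that SAP 7.2 has a related fault, since it counts a medication as concomitant if it "starts within the analysis phase of the respective treatment". The documents do not support that. The section defines when a medication counts as concomitant, and Protocol 7.3.4 presents such therapies without regard to intervals or periods.

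**Conclusion.** The point holds as a wording defect with a limited reach. Read with the protocol's formulation names, the end rule leaves the period 5 fasted phase open through period 6 and follow-up in exactly two of ten sequences. The expected number of subjects is 4.8, or 4 to 6 if blocks of 10 were used. These counts assume the planned 24 subjects, with no dropouts or replacements.

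Three stronger readings are tempting and are not supported:

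- **That double counting will occur.** The text is ambiguous, the intent is probably the next dose, and the programming specification has not been seen.
- **That events after the fed dose would count only as fasted.** The start rule opens a phase at a dose in any formulation, so the literal result is assignment to both.
- **That the food-effect result is compromised.** That comparison is of PK endpoints and does not use these phases. Laboratory and vital-sign summaries are pooled in a single column and are also unaffected.

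What remains exposed is the set of descriptive by-treatment AE tables. Correcting a stated rule that feeds them is worth the small effort.

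**What to change.** In SAP Table 6.1: 1, in the end column of the on-treatment row, replace "Date/time of administration of BI 894416 in another formulation" with *Date/time of next administration of BI 894416 (next treatment period)*. Keep the trial-termination limit as it is. Confirm that the derivation of AE phases in the dataset specification follows the same rule. Make no change to SAP 7.2.

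The cost is one line of SAP wording and, if needed, the matching line of code. No new data are required, and the eight unaffected sequences keep the same phase boundaries.
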